## 6.6.2. NA Re-treatment Criteria and Monitoring After Stopping of NA

Participants who meet the NA treatment completion criteria outlined in Section 6.6.1, Study Intervention Completion at Consolidation Week 12, will be monitored closely during the follow-up phase.

After stopping NA treatment, participants should be monitored as follows:

- Regular monitoring visits will be every 4 weeks during the follow-up phase in accordance with the Schedule of Activities.
- A post-treatment HBV DNA value of >20,000 IU/mL should trigger re-testing of ALT/AST, HBV DNA, and total and direct bilirubin within a maximum of 7 days from receipt of the data and further repeats as necessary (ie, weekly until HBV DNA returns to <20,000 IU/mL).
- A post-treatment HBV DNA value of >2,000 IU/mL (but <20,000 IU/mL) should trigger a re-test within 14 days from receipt of the data and further repeats as necessary (ie, every other week until HBV DNA returns to <2,000 IU/mL).
- A post-treatment ALT value of >5x ULN should trigger re-testing of ALT, AST, ALP, total and direct bilirubin, INR, albumin, and HBV DNA on a weekly basis until ALT and AST levels have returned to <5x ULN.

After stopping NA treatment, participants should re-start NA treatment:

- Immediately with signs of decreasing liver function based on laboratory findings (eg, International Normalized Ratio [INR], direct bilirubin) or clinical assessment (eg, ascites, hepatic encephalopathy).
- Immediately with an HBV DNA value of >100,000 IU/mL (irrespective of confirmation and/or ALT increase).
- With confirmed post-treatment HBeAg seroreversion (HBeAg positive after it was negative at NA completion).
- With confirmed\* post-treatment increases in HBV DNA >2,000 IU/mL and ALT >5x ULN.

- With confirmed\* post-treatment increases in HBV DNA >20,000 IU/mL.
- \* At least 4 weeks apart frequency of visits as described above

*Note*: Additional re-testing and/or earlier restarting of NA treatment is at the investigator's discretion, even if the above cut-offs are not yet met.

To avoid delays in decision making, sites are encouraged to run local re-testing in parallel with central re-testing in the situations described above that require more frequent re-testing. Local test results are to be recorded in the CRF and/or source documents, including information on the HBV DNA assay used. In addition, to avoid delays in NA re-treatment, it should be considered to dispense NA to participants who potentially met the NA re-treatment criteria (eg, pending confirmation) and who will not be available to come to the study site immediately at the time the confirmatory test results will become available. This should ensure that the participant can immediately re-start NA treatment if indicated, upon direct confirmation by the investigator.

In case NA treatment is re-started, participants will be followed until the end of the study or until clinical stabilization, whichever comes later.

Refer to Appendix 16 in Section 10.16 for a graphical representation.

## 6.7. Study Intervention After the End of the Study

Refer to Section 6.7 of the Master Protocol PLATFORMPAHPB2001.

The investigator should consider to re-start NA treatment per local standard of care at the EOS visit (Follow-up Week 48) for participants who met the NA treatment completion criteria at Consolidation Week 12, who did not re-start NA treatment during the follow-up phase, and who did not achieve and maintain HBsAg seroclearance. NA will not be provided by the sponsor after the final study visit.

# 7. DISCONTINUATION OF STUDY INTERVENTION AND PARTICIPANT DISCONTINUATION/WITHDRAWAL

If a participant discontinues study intervention for any reason before consolidation Week 12, the participant will have an early withdrawal visit and will enter follow-up unless he/she withdraws consent. If the reason for withdrawal from the study is withdrawal of consent, then the participant will be offered an optional safety follow-up visit. Study intervention assigned to the participant who discontinued study intervention may not be assigned to another participant.

# 7.1. Discontinuation of Study Intervention

With the implementation of Protocol Amendment 6, all participants had to stop JNJ-6379 treatment immediately.

Treatment with JNJ-3989 and PegIFN- $\alpha$ 2a must be discontinued before consolidation Week 12 for all reasons listed in Section 7.1 of the Master Protocol PLATFORMPAHPB2001 and for all additional intervention-specific reasons. All the discontinuation criteria are listed below and the intervention-specific criteria are highlighted (colored fill). For the few criteria from the Master

Protocol that are specified or more restricted in this ISA, the changes compared to the Master Protocol are also highlighted (colored fill). If JNJ-3989 is discontinued, PegIFN- $\alpha$ 2a should also be discontinued. If PegIFN- $\alpha$ 2a is discontinued, JNJ-3989 should be continued. NA treatment may be continued or, in consultation with the sponsor, discontinued based on investigator judgement.

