- a. All follow up study visits are to be scheduled relative to the last dose of JNJ 3989/PegIFN α2a. An unscheduled visit can be performed upon the investigator's discretion, in case of HBV DNA elevations, ALT elevations, other signs of worsening of liver disease, or for any other reason during follow up.
- Participants who withdraw consent during follow up will be offered an optional safety follow up visit.
- c. Participants who discontinue study intervention early will have an early WD visit and will enter follow up unless they withdraw consent. Participants who withdraw consent during study intervention will be offered an optional safety follow up visit to occur on the day of consent withdrawal. For the optional safety follow up visit, assessments are at the investigator's discretion and could be similar to the early WD visit.
- d. Follow up Week 8, 16, 20, 28, 32, 40, and 44 visits are not required for participants who did not complete NA treatment at Follow up Week 2 and for participants who have restarted NA treatment during the follow up period, provided that their HBV DNA and ALT values are stable.
- e. In between study visits, participants will take NA orally at home and will bring their NA with them to each study visit. At study visits, NA should be taken on site. PegIFN α2a should be administered weekly, preferably in the evening by self injection. If desired, participants can also choose to have the weekly administration of PegIFN α2a performed on site irrespective of the time of day. PegIFN α2a should preferably be administered in the evening prior to the sparse PK visit, or alternatively in the morning of the visit on site.

- f. No JNJ 3989/PegIFN α2a will be administered or dispensed during follow up. Administration/Dispensation of NA is only applicable for participants who could not stop NA treatment, or for those who met the NA re treatment criteria. In between study visits, participants will take NA at home and they will bring their NA treatment with them to each study visits, the NA treatment should be taken on site.
- g. If the NA treatment completion criteria are met at consolidation Week 12, treatment with NA will be completed at FU Week 2.
- h. Complete physical examination, including body weight, skin examination, and other body systems.
- i. Vital signs include supine SBP, DBP, pulse rate, and body temperature.

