The investigator should consider to re-start NA treatment per local standard of care at the EOS visit (Follow-up Week 48) for participants who met the NA treatment completion criteria at Consolidation Week 12, who did not re-start NA treatment during the follow-up phase, and who did not achieve and maintain HBsAg seroclearance. NA will not be provided by the sponsor after the final study visit.

If a participant prematurely (before the end of the consolidation phase) discontinues JNJ-3989, follow-up assessments should be obtained as per the Schedule of Activities until 48 weeks after the end of investigational intervention unless the participant withdraws consent. If a participant prematurely discontinues PegIFN-α2a (before the end of the consolidation phase), treatment with JNJ-3989 and NA should be continued as planned. In case the participant withdraws consent, NA treatment may be continued or, in consultation with the sponsor, discontinued, based on the above mentioned NA treatment completion criteria.

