the participant should discontinue JNJ-3989 and PegIFN-α2a and should be monitored on a weekly basis or as per good clinical practice until ALT and AST levels have returned to <5x ULN, HBV DNA is <20,000 IU/mL, and, if present, liver-related symptoms have improved. NA treatment should be continued. Additional tests can be considered based on clinical judgement (Refer to Section 10.6, Appendix 6, Intervention-emergent ALT/AST Elevations).

In case of prolonged ALT elevation >3x ULN AND >2x nadir, which lasts at least 12 weeks, the decision to continue JNJ-3989 and PegIFN- $\alpha$ 2a should be based upon virologic parameters (eg, HBsAg, HBV DNA) and should be made in consultation with the sponsor.

PegIFN- $\alpha$ 2a may need to be discontinued in clinically significant cases of ALT increase or in combined increase of ALT and direct bilirubin. Refer to the prescribing information for PegIFN- $\alpha$ 2a. 

The NA re-treatment criteria and monitoring after stopping of NA are presented in Section 6.6.2.

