## 8.3.6.4. Hematologic Abnormalities

Mild thrombocytopenia was observed in recently conducted non-clinical toxicology studies with the combination of JNJ-3989 and JNJ-6379. In addition, in a 3-month combination study with 80 rats, 1 rat developed pancytopenia related to bone marrow depletion after 23 days of dosing. Previously, in a 9-month dog study in 24 dogs treated with JNJ-6379 alone, pancytopenia which correlated with a marked increase in plasma cell-like cells in the bone marrow was observed in 1 dog after 60 days of dosing.

No thrombocytopenia or pancytopenia has been observed in the ongoing Jade study (56136379HPB2001) investigating JNJ-6379/Placebo with or without NA treatment. All 232 participants have completed at least 24 weeks of study intervention. In the Phase 1/2a AROHBV1001 study with JNJ-3989, mild transient thrombocytopenia (Grade 1) was observed in 6 out of 84 participants receiving 3 SC injections of JNJ-3989 alone over a period of up to 12 weeks with background of NAs. The transient thrombocytopenia was not considered clinically significant. No thrombocytopenia or pancytopenia was observed in 12 participants when JNJ-3989 and JNJ-6379 were given in combination over a 12-week period.

Based on the non-clinical findings, any relevant abnormalities in hematologic parameters will be carefully monitored as described below:

- Platelet counts: <100,000 cells/mm^3 or <100 GI/L or reduction from baseline by at least 50%
- Hemoglobin: Decrease of at least 2 g/dL from baseline or at least Grade 2 (DAIDS)
- Reticulocytes: Reduction to <0.5% of the RBC count
- Neutrophil count: Treatment emergent reduction to at least Grade 2 (DAIDS)

In case any one of the above criteria are met, a confirmatory visit should be scheduled as soon as possible, preferably within 7 days of the receipt of the initial results. Confirmation of the results will trigger weekly or biweekly (every other week) unscheduled visits until improvement or stabilization of the respective parameter(s). Stabilization is defined as no further significant reduction over two consecutive visits.

In case of confirmed Grade 3 or Grade 4 hematologic abnormalities, discontinuation of treatment with JNJ-3989 and PegIFN- $\alpha$ 2a should be considered. In case of discontinuation, NA treatment should be continued.

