## 1.5. Randomization and Blinding

### Randomization

For participants in Cohort 1, a distinction will be made depending on the timing when the ISA protocol Amendment #6 will be in effect. Protocol Amendment #5 was not implemented due to the USM and no participants will be receiving Protocol Amendment #5 treatment.

- If a participant of Cohort 1 is in between Week 36 and 60 and met the RGT criteria prior to Amendment #5 approval, then he/she will be randomly assigned in a 1:1 ratio to 1 of 2 intervention arms (Arm 1 = JNJ-3989+JNJ-6379+NA+PegIFN- $\alpha$ 2a; or Arm 2 = JNJ-3989+JNJ-6379+NA). The randomization is stratified by screening HBV DNA level ( $\geq 10^7$  IU/mL OR  $<10^7$  IU/mL) and timing of meeting the study defined RGT criterion (at Week 36 OR after Week 36 up to Week 48 OR after Week 48 up to Week 60 OR not met before or at Week 60) for participants in Cohort 1.
- If a participant of Cohort 1 has not yet reached Week 36, or did not meet RGT criteria up to Week 60 prior to Amendment #5 approval, then he/she will not be randomized, but will have PegIFN- $\alpha$ 2a added to his/her treatment regimen at the next scheduled visit. After 12 weeks, treatment with NA, PegIFN- $\alpha$ 2a, JNJ-3989 and JNJ-6379 will be stopped, regardless of the actual duration of induction (which may exceed 36 weeks).

For participants in Cohort 2 as of Protocol Amendment #6, the study will continue as a single-arm study (JNJ-3989+NA+PegIFN- $\alpha$ 2a). All newly enrolled participants will receive JNJ-3989+NA for 36 weeks (induction phase) and will then enter the 12-week consolidation phase during which they will have PegIFN- $\alpha$ 2a added to their treatment regimen.

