##### **5.3.2.1.1.2. NA Re-Treatment Criteria and Monitoring After Stopping of NA**

The number and proportion of participants who meet the criteria for NA re-treatment at any time during FU will be summarized descriptively by cohort. Only the subset of ITT participants who meet the NA treatment completion criteria at any time during the study and actually stop NA treatment will be included in the analysis (as defined in Section 5.3.1.1.2.2).

The proportion of participants who actually re-started NA treatment and monitoring after stopping of NA on the basis of the ‘Study Drug Administration for NA’ CRF page will be summarized separately over time by cohort.

In addition, the proportion of participants who met the above criteria according to the flag on the CRF page of 'NA Re-treatment Criteria Assessment' during the follow-up phase will be summarized over time by cohort.

A cross-tabulation of participants who actually re-started NA treatment (re-started/not restarted) versus participants versus participants who met the above criteria (met/not met) will be presented over time.

A listing including all participants who meet the NA re-treatment criteria and monitoring after stopping of NA will be generate. This listing will also include information whether they actually re-started NA treatment (re-started/not restarted).

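### Protocol 7.1 allows NA to be stopped in ALT/AST and cytopenia cases where 8.3.6.2 and 8.3.6.4 say to continue it, and the SAP states an unconditional NA stop for part of Cohort 1 that the protocol does not contain

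*Protocol*

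**What the plan says.** Protocol 7.1 states its NA rule once, ahead of the whole list of discontinuation criteria: "NA treatment may be continued or, in consultation with the sponsor, discontinued based on investigator judgement". The list includes ALT/AST elevations, with a pointer to 8.3.6.2, and confirmed grade 3 or higher hematologic abnormalities, with a pointer to 8.3.6.4. No exception is made for either.

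For ALT/AST elevation with signs of reduced liver function, 8.3.6.2 stops JNJ-3989 and PegIFN and adds: "NA treatment should be continued. Additional tests can be considered based on clinical judgement". It gives the same NA direction for isolated elevations and for confirmed ALT above 1,000 U/L. For cytopenia, 8.3.6.4 says: "In case of discontinuation, NA treatment should be continued". Section 6.6.1 has a further sentence on NA, about participants who withdraw consent: "NA treatment may be continued or, in consultation with the sponsor, discontinued, based on the above mentioned NA treatment completion criteria".

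For Cohort 1 participants who were not randomized before Amendment 5, SAP 1.5 says: "After 12 weeks, treatment with NA, PegIFN- $\alpha$ 2a, JNJ-3989 and JNJ-6379 will be stopped, regardless of the actual duration of induction". The text under SAP Figure 2 says much the same of participants who had passed Week 36 or had been randomized to the group without PegIFN.

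On visits, footnote d to Protocol 1.3.2 says that seven named follow-up "visits are not required for participants who did not complete NA treatment at Follow up Week 2", or who have restarted NA, on condition that HBV DNA and ALT are stable. Section 6.6.2 says, for participants after stopping NA: "Regular monitoring visits will be every 4 weeks during the follow-up phase in accordance with the Schedule of Activities".

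On analysis, the summary of participants meeting the NA re-treatment criteria in SAP 5.3.2.1.1.2 includes: "Only the subset of ITT participants who meet the NA treatment completion criteria at any time during the study and actually stop NA treatment".

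**The concern.** An investigator whose participant stops JNJ-3989 for an ALT flare or a cytopenia finds two answers on background NA: a discretionary one in 7.1 and a directive one in the section that 7.1 cites. The same situation could be handled differently from one case to the next, with each handling defensible from the text.

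This matters because the protocol treats NA withdrawal as hazardous. Section 4.2 explains that Amendment 6 tightened monitoring and re-treatment rules after a severe clinical flare following NA discontinuation in a related study. Someone who stops NA under 7.1 need not have met the completion criteria, so the visit rules and the re-treatment summary, both built around participants who complete NA by those criteria, may not cover them clearly.

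The SAP conflict is different in kind. It describes a treatment rule that the protocol does not contain, so NA exposure and off-treatment status in part of Cohort 1 could be derived or interpreted on a wrong premise.

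**Working it through.** The plan states no figure on this point. The check is a comparison of texts, plus a count of visits.

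**1. NA after an early stop of JNJ-3989**

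| Reason for stopping | Protocol 7.1 | Specific section |
|---|---|---|
| ALT/AST elevation | NA may be continued or stopped | 8.3.6.2: NA should be continued |
| Confirmed grade 3 or higher cytopenia | NA may be continued or stopped | 8.3.6.4: NA should be continued |
| Grade 3 or 4 rash, allergic reaction | NA may be continued or stopped | Appendix 5 and 8.3.7.2: NA may be stopped on judgement, with sponsor consultation |

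The first two rows conflict and the third agrees. The specific sections therefore distinguish between reasons, and the single rule in 7.1 does not.

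**2. JNJ-3989 and PegIFN in cytopenia.** Section 7.1 says that they must be discontinued for its listed reasons, which include confirmed grade 3 or higher hematologic abnormalities. Section 8.3.6.4 says that discontinuation should be considered. These also conflict.

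**3. SAP against protocol, Cohort 1.** SAP 1.5 and the text under SAP Figure 2 include NA among the drugs stopped after 12 weeks. The matching protocol sentences (1.1 Overall Design, 1.2 Figure 2, 4.1) name PegIFN, JNJ-3989 and JNJ-6379, but not NA. Protocol 4.1 and 6.6.1 stop NA at FU Week 2 only if all four completion criteria are met at Consolidation Week 12 (with a discretionary note on ALT), and otherwise continue it. Footnote a to SAP Figure 2 and the later text of SAP 1.2 follow the protocol, so the SAP also contradicts itself.

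**4. Visits under footnote d.** The full schedule has FU Weeks 2, 4, 8, 12, 16, 20, 24, 28, 32, 36, 40, 44 and 48: 13 visits, with a longest gap of 4 weeks. Removing Weeks 8, 16, 20, 28, 32, 40 and 44 leaves 13 − 7 = 6 visits (Weeks 2, 4, 12, 24, 36, 48), with gaps of 2, 8, 12, 12 and 12 weeks.

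Who may skip them? Footnote d names those who did not complete NA at FU Week 2, and literally that includes someone who stopped NA at an early withdrawal visit. Three other places point the other way. The note at the head of 1.3.2 gives fewer visits to those who could not stop NA. The blood-volume note in Section 8 ties the optional visits to those continuing or having restarted NA. The list in 6.6.2 applies after stopping NA. However, the opening sentences of 6.6.2 and Appendix 16 speak only of participants who meet the completion criteria.

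**5. The re-treatment summary.** A participant is outside it if they never met all four completion criteria, or if they are outside ITT, which requires at least one consolidation-phase dose (SAP 2.3). The SAP foresees NA stops other than at FU Week 2: SAP 4.6 provides for participants who stopped NA at or before Consolidation Week 12. The SAP Amendment 4 rationale reports one participant who met the criteria and stopped NA at that visit. That is a count at one visit, whereas the summary takes in those who met the criteria at any time, so its denominator is not shown to be 1.

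**The case against.** The best defence is that 7.1 states a default and the specific sections override it. The default is permissive, the two bullets refer the reader to 8.3.6.2 and 8.3.6.4, and stopping NA needs consultation with the sponsor, which makes divergent handling less likely. This lowers the practical risk but does not remove the conflict, because 7.1 nowhere says that the cited sections take precedence.

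It is also fair that the 6.6.1 sentence concerns withdrawal of consent. It is not a competing rule for ALT or cytopenia stops. SAP 1.5 looks like a drafting slip, since other SAP text agrees with the protocol; it still needs correcting.

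A reader might infer that anyone who stops NA under 7.1 escapes the 4-weekly visits. The documents do not support that. The head note, Section 8 and 6.6.2 point the other way, and the waiver needs stable HBV DNA and ALT. Participants with ALT elevation are monitored weekly until resolution (or, with reduced liver function, weekly or per good clinical practice), and those with confirmed cytopenia weekly or every other week.

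A reader might also infer that such participants vanish from the re-treatment analysis and bias it downward. That is too strong. The restriction is stated for one summary. The same SAP section plans CRF-based summaries of actual restart and of criteria met, a cross-tabulation and a listing, none of which repeats it. The disposition listing in SAP 4.1 also records NA discontinuation and re-treatment. In a descriptive study without a formal hypothesis, a denominator of protocol-defined completers is a legitimate choice.

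**Conclusion.** Three contradictions stand in the current text: 7.1 against 8.3.6.2 and 8.3.6.4 on NA; 7.1 against 8.3.6.4 on whether JNJ-3989 and PegIFN must be stopped for confirmed grade 3 or higher cytopenia; and SAP 1.5 with the text under SAP Figure 2 against the protocol, and against the SAP itself, on stopping NA in Cohort 1. They need reconciling because they concern a drug whose withdrawal the protocol links to a severe flare.

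Footnote d is an ambiguity. Its largest effect, 6 visits instead of 13 with gaps of up to 12 weeks, assumes the literal reading and stable HBV DNA and ALT.

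The effect on the re-treatment summary is possible but not shown, because no document reports anyone who stopped NA under 7.1. It might be tempting to argue from the single participant at Consolidation Week 12 that each omitted case changes the denominator by half or more. That does not follow: the denominator is not shown to be 1, and even from 1 the successive additions are 100%, 50% and then 33% (1 to 2, 2 to 3, 3 to 4). The definition of the primary endpoint is not affected.

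**What to change.** The sponsor should choose the clinical rules and make the texts agree:

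- Reconcile Protocol 7.1 with 8.3.6.2 and 8.3.6.4, both on NA and on mandatory versus considered discontinuation of JNJ-3989 and PegIFN, and state which section governs.
- Reconcile SAP 1.5 and the text under SAP Figure 2 with the protocol's rule on NA completion.
- Reconcile footnote d with the head note of 1.3.2, 6.6.2 and the note in Section 8, so that the follow-up schedule is explicit for a participant who stopped NA outside the completion criteria.
- In SAP 5.3.2.1.1.2, add a row for participants who stopped NA without meeting the completion criteria, including any outside ITT, shown separately from those who met them. A zero count should be reported as such.

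The cost is a protocol clarification, a few SAP sentences and one table row. Depending on how the sponsor resolves footnote d, a few participants might attend follow-up visits that are already in the schedule.
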